4.1.17. Maximum Tolerated Dose (Final Dose Level)

The final dose level is defined as the dose received at the Week 26 timepoint or at the time of early termination if the subject achieved a minimum of 5 mg prior to discontinuation.

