The titration schedule, as shown in [Table 4](#), will be used for all subjects who are randomized to receive tavapadon. Subjects will take 3 tablets of IMP, either all tavapadon tablets, all placebo tablets, or a combination of tavapadon and placebo tablets, throughout the trial to maintain the trial blind.

Table 4 Tavapadon and Placebo Dosing Schedule

Trial Day	Titration Step	Blinded Treatment Assignment
		Maintenance Phase^c
		Maximum tolerated tavapadon dose (5-15 mg) or placebo QD

Abbreviation: QD = once daily.

- a. No deviations in the titration schedule up through 5 mg QD [REDACTED] will be allowed.
- b. The dose will be adjusted over the range of 5 to 15 mg [REDACTED] based on individual subject tolerability.
- c. Subjects will receive the highest tolerated dose level that is achieved during the Dose Adjustment Phase. No adjustment in the tavapadon dose will be allowed during the Maintenance Phase.

No deviations in the titration schedule up through [REDACTED] (5 mg QD) will be allowed. Titration of tavapadon should be guided by absence of tolerability issues that are reported as AEs and that are of sufficient severity resulting in significant dysfunction or distress to the subject. Any questions regarding tolerability issues and titration should be directed to the medical monitor before adjustments are initiated. The dose of tavapadon will be gradually titrated to the [REDACTED] dose (15 mg QD) in all subjects, as shown [Table 4](#), unless prevented by intolerance.

Subjects who are unable to achieve or tolerate the [REDACTED] dose (15 mg QD) may receive the [REDACTED] dose (10 mg QD). Subjects who cannot achieve or tolerate the [REDACTED] dose (10 mg QD) may receive the [REDACTED] dose (5 mg QD). Subjects who cannot achieve or tolerate the [REDACTED] dose (5 mg QD) will be discontinued from the trial. Subjects who require a dose reduction may be rechallenged with a higher dose to address symptomatic needs after at least 7 days at the lower dose during the Dose Adjustment Phase.

Subjects will receive the highest tolerated dose level that is achieved during the Dose Adjustment Phase for the duration of the subsequent 13-week Maintenance Phase. Adjustments in the dose of tavapadon will not be allowed during the Maintenance Phase. Subjects who cannot tolerate their maintenance dose will be discontinued from the trial.

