Subjects will receive the highest tolerated dose level that is achieved during the Dose Adjustment Phase for the duration of the subsequent 13-week Maintenance Phase. Adjustments in the dose of tavapadon will not be allowed during the Maintenance Phase. Subjects who cannot tolerate their maintenance dose will be discontinued from the trial. Subjects will be considered to have completed this trial once they complete the assessments that are scheduled at the Week 27 visit.

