5.8. Exposure to Treatment

The number of days on study drug, reasons for premature discontinuation of IMP, treatment compliance, days in each phase (Titration, Adjustment, and Maintenance), average dose in each phase, average L-Dopa dose during treatment period, and maximum tolerated dose will be summarized by treatment group for the FAS Population.

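### SAP 4.1.17 defines maximum tolerated dose as the last dose taken, whatever the reason for stopping, so some subjects are tabulated as tolerating a dose they were withdrawn for not tolerating

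*SAP*

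**What the plan says.** The heading of SAP 4.1.17 names maximum tolerated dose and gives final dose level in brackets as the same thing. One definition serves both: "The final dose level is defined as the dose received at the Week 26 timepoint or at the time of early termination". The early-termination part carries a single condition: "or at the time of early termination if the subject achieved a minimum of 5 mg prior to discontinuation". Neither tolerability nor the reason for stopping enters the rule.

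SAP 5.8 lists the variable among the exposure summaries: "and maximum tolerated dose will be summarized by treatment group for the FAS Population". SAP 5.9.3.1 uses the same rule for a by-dose sensitivity analysis of efficacy, but there calls it final dose level only.

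The dosing rules are in Protocol 4.1.2 and are repeated in SAP 1.4. Subjects who cannot achieve or tolerate 5 mg are discontinued. In maintenance, "Adjustments in the dose of tavapadon will not be allowed during the Maintenance Phase", and "Subjects who cannot tolerate their maintenance dose will be discontinued from the trial".

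The documents also have a notion of the tolerated dose of their own. Table 4 of the protocol (Table 1 of the SAP) labels the Maintenance Phase dose as the maximum tolerated dose, and note c explains it: "Subjects will receive the highest tolerated dose level that is achieved during the Dose Adjustment Phase".

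**The concern.** A dose tolerated and a dose last taken are different quantities. They agree for a subject who completes Week 26 on the maintenance dose. They can part for a subject who stops early, because the dosing rules make intolerance a cause of stopping. The dose cannot be lowered in maintenance, so a subject withdrawn there for intolerance leaves on the dose that failed. The same holds for a subject withdrawn because 5 mg, once reached, could not be tolerated.

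The trial is flexible-dose and aims to define the risk/benefit profile over 5 to 15 mg. A row headed maximum tolerated dose will be read as showing which doses subjects could stay on. What is at stake is the correct reading of that row. The hypothesis tests are not involved.

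**Working it through.** There is no stated figure to reproduce, because the point concerns a derivation rule. The check applies the rule to each kind of subject the dosing rules allow, then bounds the number affected.

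**Step 1. Value assigned in each case**

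| Subject | Value under SAP 4.1.17 | Is it a tolerated dose? |
|---|---|---|
| Completes Week 26 on the maintenance dose | That dose | Yes |
| Steps down in Dose Adjustment, later leaves maintenance for an unrelated reason | The lower dose | Yes |
| Withdrawn in maintenance because the maintenance dose is not tolerated | The dose that failed | Only in the sense of Table 4 note c; not over the subject's whole course |
| Reaches 5 mg, withdrawn because 5 mg is not tolerated | 5 mg | No |
| Leaves during Dose Adjustment at 5 mg or more for an unrelated reason | Level in use on leaving | Not a tolerability limit; a higher level may not have been tried |
| Stops before reaching 5 mg | None | Not applicable |

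The third and fourth rows carry the misreporting. The fifth gives a value that does not mean what its label says. The last drops the subject from the variable.

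**Step 2. Upper bound on the early-termination branch**

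Inputs from SAP 1.2: 184 subjects per arm and 27% dropout for all reasons. I apply the 27% equally to each arm.

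- Branch size ≤ arm size × dropout = 184 × 0.27 = 49.7, about 50 subjects.
- At the re-estimation ceiling of 528 (264 per arm): 264 × 0.27 = 71.3, about 71 subjects.

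This is an upper bound because dropouts who stop before 5 mg get no value and are not on the branch.

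**Step 3. Subjects recorded as tolerating a failed dose**

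Let s be the share of the branch that stops for intolerance at 5 mg or more. The documents do not give s, so the values below are assumptions. Affected ≤ 184 × 0.27 × s:

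| s (assumed) | Subjects, of 184 | Share of arm | Subjects, of 264 |
|---|---|---|---|
| 10% | 5.0 | 2.7% | 7.1 |
| 25% | 12.4 | 6.8% | 17.8 |
| 50% | 24.8 | 13.5% | 35.6 |

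**Step 4. Direction**

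Recording a failed 10 mg or 15 mg as tolerated pushes the distribution up. Giving unrelated leavers in Dose Adjustment the level they happened to be on pulls it down. A failed 5 mg adds to the lowest category. Leaving out subjects who stopped below 5 mg removes early failures from the table; if doses are tabulated as categories, the convention in SAP 9.5 of using the displayed total as denominator would remove them from the percentages too. The documents give no counts for these groups, so the net direction cannot be derived.

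**The case against.** The strongest reply is that the SAP follows the protocol's own term. Table 4 calls the maintenance dose the maximum tolerated dose, note c ties it to the Dose Adjustment Phase, and no change is allowed afterwards. For anyone who enters maintenance, the dose at termination therefore equals the protocol's maximum tolerated dose. This stands as far as it goes: a maintenance dropout's value matches one usage in the documents. But SAP 4.1.17 does not state that definition, and it does not rescue the subject withdrawn because 5 mg failed or the subject who leaves before maintenance.

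A second reply is that intolerance is reported elsewhere. SAP 5.8 gives reasons for premature discontinuation in the same exposure summary. SAP 5.15.1 adds events leading to discontinuation, events leading to dose reduction, and events by phase and by dose at onset. SAP 5.6 adds a Kaplan-Meier plot of discontinuation due to adverse events, and Protocol 8.4.6.3 requires narratives. This also stands, and it limits the harm. None of these summaries corrects the row labelled maximum tolerated dose.

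A reader might infer more than the documents support:

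- *Every intolerance withdrawal is counted as tolerance.* It is not, because subjects who stop below 5 mg get no value.
- *The table is biased towards better tolerability.* Step 4 shows opposing effects, and the net is unknown.
- *All of the roughly 50 early terminators are misreported.* That figure covers all reasons for dropout and is only a ceiling on the branch.
- *The efficacy results are affected.* The variable plays no part in the primary or key secondary test, and the by-dose sensitivity analysis already uses the neutral name.

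**Conclusion.** The point holds as a mislabelled descriptive variable. SAP 4.1.17 makes maximum tolerated dose equal to the last dose regardless of the reason for stopping, and SAP 5.8 reports it under that name. Subjects discontinued because they could not tolerate 5 mg after reaching it, or their maintenance dose, are tabulated at the dose that failed. The 5 mg case is wrong on any reading. The maintenance case is wrong as a statement about the whole course, though it agrees with the Table 4 usage.

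The size rests on two assumptions: that the planned 27% dropout applies to the tavapadon arm, and that 10% to 50% of the early-termination branch stops for intolerance at 5 mg or more. Under these, at most about 5 to 25 of 184 subjects are affected. The second assumption has no source in the documents; the mechanism does not depend on it. The consequence is confined to one exposure table. The change is worth making because it costs almost nothing.

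**What to change.** In SAP 4.1.17 and 5.8, call the current variable final dose level only.

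If maximum tolerated dose is also reported, define it separately as the dose level assigned at the end of the Dose Adjustment Phase, which is the Table 4 usage. State the day that marks that point: SAP 1.1 ends titration and adjustment at 13 weeks, while SAP 1.4 and Protocol 4.1.2 say 14, and these passages need to be reconciled.

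Cross-tabulate final dose level by completion status and discontinuation reason (adverse event, other):

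- Add a row for subjects who stopped below 5 mg, and one labelled stopped before maintenance: not established.
- Take the other dose rows from the dosing schedule, since its steps are partly blacked out in the public copy and 5, 10 and 15 mg may not be exhaustive.
- Label the adverse-event rows as discontinued for AE at this dose, not as not tolerated. The reason listed in Protocol 7.3 is adverse event, which need not mean intolerance of the current dose.
- Use all FAS subjects in the arm as the denominator.

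The cost is SAP wording and one table built from dosing and discontinuation data already collected. The table may look slightly less favourable. No dosing or withdrawal rule changes.

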4.1.18. Compliance with Study Drug

Accountability and compliance will be assessed through self-reporting by the subject and by tablet count at each clinic visit. For analysis purposes, evaluation of compliance will be based on the site assessment of compliance as recorded on the DRUG ACCOUNTABILITY eCRF. Compliance will be calculated as a percentage based on the total number of tablets taken relative to the total expected number of tablets based on days on study. If a kit was lost and return information was available, the return information will be used for the compliance calculation. If a kit was lost and no return information was available, it is assumed that the tablets were not taken for the compliance calculation. If return information is not available and the kit was not lost, it is assumed that the tablets were taken for the compliance calculation.

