4.1.3 Safety Follow-up Period

Subjects who complete through Week 27 of the trial may have the opportunity to enter an open-label extension trial (Protocol CVL-751-PD-004). Subjects who are ineligible or elect not to enter the open-label trial will be contacted by telephone at 4 weeks after discontinuation of trial treatment (either after completing the full 27-week treatment period or upon premature discontinuation from the trial).

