4.4 Definition of Completed Subject

Subjects will be considered to have completed this trial once they complete the assessments that are scheduled at the Week 27 visit.

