6.3 Measures to Minimize Bias: Randomization and Blinding

6.3.1 *Subject Assignment to Treatment*

All subjects will be centrally randomized in a 1:1 ratio to 2 treatment arms (tavapadon 5 to 15 mg QD or placebo) at the Baseline Visit via an Interactive Voice Response System/Interactive Web Response System (IVRS/IWRS), according to a computer-generated randomization scheme. Subjects will be sequentially assigned to the next available randomization number and will receive the IMP that corresponds to that randomization number. Once a randomization number has been assigned, it will not be reassigned.

The telephone number and call-in directions for the IVRS and/or the log-in information for and directions for the IWRS will be provided to each trial site before the trial is initiated.

6.3.2 *Blinding*

The tavapadon and placebo tablets will be identical in appearance and will be packaged in identically appearing blister cards. All subjects will take 3 tablets once daily of IMP during the Treatment Period, either all tavapadon tablets, all placebo tablets, or a combination of tavapadon and placebo tablets. Tablets will be packaged to allow dosage adjustments (as shown in [Table 4](#)) to be made without breaking the trial blind.

Treatment assignments will be blinded to the investigators and other trial site personnel, the subjects, and all sponsor personnel who are involved in the conduct of the trial (including trial monitoring, data management, and data analysis). Access to the treatment codes will be restricted to personnel who are responsible for generating and maintaining the randomization code, packaging the IMPs, operating the IVRS/IWRS, analyzing the PK blood samples, or reporting serious adverse events (SAEs) or adverse events of special interest (AESI) to regulatory agencies.

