6.4 Trial Treatment Compliance

All IMP will be dispensed by responsible trial personnel. Subjects will be counseled on the importance of taking the IMP as directed (once daily in the morning, with or without food) at each clinic visit and will be instructed to bring all used and unused blister cards to each clinic visit. Accountability and compliance (as assessed through self-reporting by the subject and by tablet count at each clinic visit) will be documented in the subject's trial records. Deviation(s) from the prescribed dosage regimen should be recorded in the eCRF.

If poor compliance is encountered (eg, multiple missed doses resulting in <80% overall compliance at any point in the trial), discontinuation of the subject from the trial should be considered. Subjects who habitually miss visits or habitually attend visits outside of the protocol-defined visit window are also defined as noncompliant and should be considered for discontinuation. The medical monitor should be contacted if the investigator is uncertain whether a subject's lack of compliance merits discontinuation from the trial.

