7.3 Individual Subject Discontinuation

After treatment assignment, a subject may stop treatment permanently for a variety of reasons. Treatment discontinuation may be initiated by a subject who is not satisfied with

treatment or may become medically necessary due to AEs, required treatment with a disallowed medication or therapy, or other issues, as determined by the investigator.

A subject may discontinue the IMP for any of the following reasons:

- Adverse event
- Death
- Worsening of PD symptoms to such an extent that, in the judgment of the investigator, the subject requires additional anti-PD medications
- Treatment with prohibited concomitant medications
- Noncompliance with study schedule
- Noncompliance with study drug
- Withdrawal by subject
- Pregnancy
- Physician decision

If a subject discontinues the IMP due to an AE, the investigator or other trial personnel will make every effort to follow the event until it has resolved or stabilized.

All subjects have the right to withdraw consent for further participation in the trial at any time without prejudice. Subjects cannot withdraw consent for use of data that have already been collected as part of the trial but can withdraw consent for future participation. The investigator can also discontinue a subject from the trial at any time if medically necessary. Unless the subject provides written withdrawal of consent or there is other written documentation by the investigator confirming the subject's verbal intent to completely withdraw from the trial, subjects should be followed for all protocol-specified evaluations and assessments, if possible.

Complete withdrawal of consent requires a subject to refuse of ALL of the following methods of follow-up:

- Participation in all follow-up procedures specified in the protocol (whether in-clinic or by telephone)
- Participation in a subset of protocol specified follow-up procedures (by a frequency schedule and method, as agreed by subject and staff)
- Contact of the subject by trial personnel, even if only by telephone, to assess current medical condition, and obtain necessary medical or laboratory reports relevant to the trial's objectives
- Contact of an alternative person(s) who has been designated in source records as being available to discuss the subject's medical condition, even if only by telephone, mail, or e-mail (eg, family, spouse, partner, legal representative [as defined per local regulations], friend, neighbor, or physician)

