4.1.5. Days on Study

Days on Study is the number of days from Day 1 to the date of study completion or early termination as recorded on the END OF STUDY eCRF.

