4.1.6. Days on IMP

Days on IMP is the number of days from Day 1 to the date of last dose of IMP as recorded on the EXPOSURE eCRF.

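### SAP 4.1.18 counts expected tablets over days on study instead of days on IMP, so compliance is understated for subjects whose last dose precedes their end-of-study date

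*SAP*

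**What the plan says.** SAP 4.1.18 calculates compliance as a percentage: the "total number of tablets taken relative to the total expected number of tablets based on days on study". It adds rules for lost kits and missing return information, and says that evaluation rests on the site's assessment on the DRUG ACCOUNTABILITY form.

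The SAP defines two intervals that could supply the denominator:
- SAP 4.1.5: "Days on Study is the number of days from Day 1 to the date of study completion or early termination", taken from the END OF STUDY form.
- SAP 4.1.6: "Days on IMP is the number of days from Day 1 to the date of last dose of IMP", taken from the EXPOSURE form.

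Section 4.1.18 uses the first. The daily tablet count is fixed in Protocol 6.3.2: "All subjects will take 3 tablets once daily of IMP during the Treatment Period". The result is summarised by treatment group on the FAS under SAP 5.8, next to days on study drug and reasons for stopping IMP. Days on study are summarised elsewhere, with disposition (SAP 5.6).

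**The concern.** Compliance should compare tablets taken with tablets due. After IMP has been stopped no tablets are due, but the rule keeps adding three a day until the subject leaves the study. The error can only lower the score.

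The documents foresee subjects who are off drug but still on study. Protocol 7.3 separates stopping IMP from withdrawing from the trial and, short of documented full withdrawal, says that "subjects should be followed for all protocol-specified evaluations and assessments, if possible". The primary estimand in SAP 5.9.1 has a rule for data collected after treatment discontinuation, which would be unnecessary if the two dates always coincided.

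At stake is the meaning of one line in the exposure table. For subjects with such a gap, the percentage mixes missed doses with time after discontinuation.

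**Working it through.** The documents state no compliance figure, so there is none to reproduce. The check follows the rule for a subject who never misses a tablet.

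Inputs:
- Tablets per day: 3 (Protocol 6.3.2).
- d: days from Day 1 to last dose, counting Day 1 (SAP 4.1.6).
- g: days from last dose to the END OF STUDY date. The documents do not give this, so it is assumed at 0, 3, 7, 14 and 28 days, with follow-up to Day 189 as an extreme.

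Formula as written: 3d / [3(d + g)] = d/(d + g).

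For a last dose on Day 35, tablets taken are 35 × 3 = 105. With exit on Day 49, tablets expected are 49 × 3 = 147 and the score is 105/147 = 71.4%. With exit on Day 63, expected tablets are 63 × 3 = 189 and the score is 105/189 = 55.6%.

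Scores for a fully adherent subject:

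| Last dose | g = 0 | g = 3 | g = 7 | g = 14 | g = 28 | Followed to Day 189 |
|---|---|---|---|---|---|---|
| Day 14 | 100% | 82.4% | 66.7% | 50.0% | 33.3% | 7.4% |
| Day 35 | 100% | 92.1% | 83.3% | 71.4% | 55.6% | 18.5% |
| Day 56 | 100% | 94.9% | 88.9% | 80.0% | 66.7% | 29.6% |
| Day 98 | 100% | 97.0% | 93.3% | 87.5% | 77.8% | 51.9% |
| Day 126 | 100% | 97.7% | 94.7% | 90.0% | 81.8% | 66.7% |
| Day 154 | 100% | 98.1% | 95.7% | 91.7% | 84.6% | 81.5% |

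The understatement grows with a longer gap and, for a given gap, with earlier stopping.

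Completers: Protocol 4.4 says "Subjects will be considered to have completed this trial once they complete the assessments that are scheduled at the Week 27 visit". Someone dosed through Day 189 who completes that day has g = 0 and scores 189/189 = 100%. The later safety call does not enter the count.

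Formula with days on IMP: 3d/3d = 100% for every d and g above.

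**The case against.** The strongest reply is that the effect depends on a gap of unknown size. Protocol 4.1.2 discontinues from the trial those who cannot tolerate the minimum or maintenance dose, and Week 27 serves as a combined end-of-treatment and early-termination visit, so the gap may often be short. That stands: with no gap the score is right, and with 3 days it is at least 82.4% from Day 14 on.

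It also stands that days on study has a use. Suppose a subject silently stops on Day 35 and is withdrawn for non-compliance on Day 63. The present rule scores 55.6%, whereas days on IMP would score 100%.

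The reference to the site's assessment does not remove the problem, because the next sentence of SAP 4.1.18 specifies the calculated percentage.

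A reader might infer more than the documents support:
- *That adherent early stoppers are classed as non-compliant against 80%.* The SAP has no compliance category, cut-off or per-protocol set. The figure comes from Protocol 6.4, where "multiple missed doses resulting in <80% overall compliance at any point in the trial" is an example to guide investigators during the trial.
- *That a 28-day gap is built in.* Subjects not entering the extension are "contacted by telephone at 4 weeks after discontinuation of trial treatment", and Table 2 note a sends early terminators into follow-up. Neither says that the END OF STUDY date is that contact.
- *That 27% of subjects, about 50 of 184 per arm, are affected.* That is the dropout allowance in the sample-size calculation. Only subjects with g > 0 are affected, and their number is unknown.
- *That the table will show a false deficit on tavapadon.* The documents give no dropout by arm. Protocol 7.3 lists worsening symptoms as well as adverse events among the reasons for stopping.
- *That discontinuation cannot be told apart from missed doses.* SAP 5.8 reports reasons for stopping IMP and days on drug alongside compliance.

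**Conclusion.** The point holds as a denominator error in a descriptive summary. As written, the rule understates compliance for every subject whose last dose precedes the END OF STUDY date, by a factor d/(d + g) if all tablets due were taken. The size for an individual runs from nothing to large, depending on the gap, and the table above shows the range under assumed gaps. The documents settle neither the number of subjects affected nor any difference between arms. Efficacy inference, the analysis populations and completers dosed to Week 27 are unaffected.

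This rests on reading days on study in SAP 4.1.18 as the interval defined in 4.1.5. If the sponsor intends the END OF STUDY date to equal the last-dose date for early terminators, the error vanishes, but neither document says so.

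**What to change.** In SAP 4.1.18, replace the reference to days on study with: *days on IMP (Section 4.1.6, counting Day 1), 3 tablets per day*. While the section is open, a sentence on how the calculated percentage relates to the site's assessment would help.

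The cost is one phrase in the SAP and one variable in the program, since both dates are already collected. The downside is that, when a subject stops taking tablets without a recorded decision to discontinue, the untaken days after the last dose leave the denominator. The compliance line should therefore be read with the reasons for IMP discontinuation and the days on study drug already summarised under SAP 5.8.

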The first dose of IMP will be taken at the trial site at the Baseline Visit; all other doses will be taken on an outpatient basis. Assessments will be conducted in the clinic at the end of Weeks 2, 5, 8, 11, 14, 18, 22, 26, and 27. Subjects will complete the Hauser diary on 2 consecutive days within the 7 days before each scheduled postbaseline clinic visit. Blood samples for PK will be collected after administration of the first dose on Day 1 (~1 hour after dosing) and at the Weeks 5, 11, 14, 22, and 27 clinic visits.

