1.3.2. Blinding

The tavapadon and placebo tablets will be identical in appearance and will be packaged in identically appearing blister cards. All subjects will take 3 tablets once daily of IMP during the Treatment Period, either all tavapadon tablets, all placebo tablets, or a combination of tavapadon and placebo tablets. Tablets will be packaged to allow dosage adjustments (as shown in [Table 1](#)) to be made without breaking the trial blind.

Treatment assignments will be blinded to the investigators and other trial site personnel, the subjects, and all sponsor personnel who are involved in the conduct of the trial (including trial monitoring, data management, and data analysis). Access to the treatment codes will be restricted to personnel who are responsible for generating and maintaining the randomization code, packaging the IMPs, operating the IVRS/IWRS, analyzing the PK blood samples, or reporting serious adverse events (SAEs) or adverse events of special interest (AESI) to regulatory agencies.

Documentation of breaking the blind should be recorded in the subject's medical record and eCRFs, with the reason for breaking the blind, the date and time the blind was broken, and the names of the personnel involved. Once the blind is broken for a subject, treatment with the IMP may not be reinitiated for that subject.

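### SAP 4.1.18 counts an unreturned kit as fully taken with no limit on dosing days, so compliance can exceed 100% in subjects who stop soon after dispensing

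*SAP*

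**What the plan says.** SAP 4.1.18 defines compliance as a percentage, the "total number of tablets taken relative to the total expected number of tablets based on days on study". The data source is the site record: "evaluation of compliance will be based on the site assessment of compliance as recorded on the DRUG ACCOUNTABILITY eCRF".

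The denominator runs on study days. SAP 4.1.5 states: "Days on Study is the number of days from Day 1 to the date of study completion or early termination". Last dose is a different variable: SAP 4.1.6 (Days on IMP) takes it from the EXPOSURE eCRF, and 4.1.18 does not use it.

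Three rules cover lost or uncounted kits:

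- Lost, but return information exists: use that information.
- Lost, with no return information: "If a kit was lost and no return information was available, it is assumed that the tablets were not taken for the compliance calculation".
- Not lost, with no return information: "If return information is not available and the kit was not lost, it is assumed that the tablets were taken for the compliance calculation".

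SAP 1.3.2 fixes the daily count: "All subjects will take 3 tablets once daily of IMP during the Treatment Period". Protocol section 4.1 sets the visits: "Assessments will be conducted in the clinic at the end of Weeks 2, 5, 8, 11, 14, 18, 22, 26, and 27". SAP 5.8 summarizes "treatment compliance, days in each phase (Titration, Adjustment, and Maintenance), average dose in each phase" by treatment group for the FAS.

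**The concern.** The numerator and denominator stop at different times. For an unreturned kit not recorded as lost, the numerator runs to the end of the kit. The denominator stops when the subject leaves the study. A subject who leaves early in a dispensing interval is credited with tablets that could not have been taken by then.

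This matters in two ways. Values above 100% are not interpretable as adherence, and they can cover poor dosing before dropout. If dropout differs between arms, the error also falls unequally in the by-arm summary.

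In addition, the same missing count earns zero tablets if the kit is recorded as lost and all of them if it is not. The SAP gives no reason for the difference.

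**Working it through.** The plan states no compliance figure, so there is none to reproduce. I applied the 4.1.18 ratio directly.

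**Inputs from the documents**
- 3 tablets a day (SAP 1.3.2).
- Scheduled visit days 14, 35, 56, 77, 98, 126, 154, 182 and 189 (SAP 9.2, Table 7).
- Expected tablets counted to early termination (SAP 4.1.18 with 4.1.5).

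**Assumptions, not in the documents**
- Each kit holds exactly one visit interval.
- All doses before the last kit were taken.
- Day 1 is counted.

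**Formula.** Let d be the day the last kit was dispensed, n the next scheduled visit day, and e the early termination day.

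Compliance = [3d + 3(n − d)] / 3e = n / e

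It exceeds 100% when termination is dated before the next scheduled visit, equals 100% on that visit day, and is below 100% afterwards.

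**Stopping 3 days after dispensing, kit not returned and not recorded as lost**

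| Last kit | Termination at last dose | Termination 28 days after last dose |
|---|---|---|
| Week 2 | 35/17 = 206% | 35/45 = 78% |
| Week 5 | 56/38 = 147% | 56/66 = 85% |
| Week 8 | 77/59 = 131% | 77/87 = 89% |
| Week 14 | 126/101 = 125% | 126/129 = 98% |
| Week 18 | 154/129 = 119% | 154/157 = 98% |

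In tablets, the first entry is 105/51. With termination 14 days after the last dose, the Week 2 case is 35/31 = 113%.

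**All stop days.** With termination at the last dose, averaging n/e over every stop day from 14 to 188 gives a mean of 117% and a median of 112%; 55% of stop days give more than 110%. Equal weighting of days is an illustration, not a forecast.

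**Smaller kit.** If the unreturned unit is a 7-day card, the ratio is (d + 7)/e: 21/17 = 124% (Week 2), 42/38 = 111% (Week 5), 63/59 = 107% (Week 8), 105/101 = 104% (Week 14) and 133/129 = 103% (Week 18).

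**Under-dosing before dropout.** With 80% of doses taken before the last kit and termination at the last dose, the ratio is [0.8d + (n − d)]/e. Stopping 3 days after dispensing gives 32.2/17 = 189% (Week 2), 49/38 = 129% (Week 5), 65.8/59 = 112% (Week 8) and 106.4/101 = 105% (Week 14).

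**Lost kit, opposite direction.** A completer who took every dose but lost one 28-day kit after using it scores (189 − 28)/189 = 85.2%; with two such kits, (189 − 56)/189 = 70.4%.

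**Limiting the numerator alone.** Take the Week 2 case with termination 28 days after a Day 17 last dose. Crediting tablets to Day 17 but leaving the denominator at Day 45 gives 17/45 = 38% for an adherent subject. Using the same days on both sides gives 17/17 = 100%.

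**The case against.** A reader might infer that early dropouts as a group will score well above 100%. The documents do not support that, for four reasons.

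- **The denominator is days on study, not days on drug.** Protocol 7.4 calls for repeated contact attempts before a subject is deemed lost, so termination may be dated well after the last dose. The ratio can then fall below 100%. This stands: the error can run either way.
- **Kit size is not given in the available text.** Protocol Table 5 mentions only blister cards. Smaller units shrink the excess. This also stands.
- **Retrieval is planned for.** Protocol 6.4 has subjects bring used and unused cards to every visit, and the Week 27 assessments, including the compliance check, apply to early dropouts. This limits how often the rule is used, but the rule exists for cases where retrieval fails.
- **The lost-kit rule can be right.** If a kit is lost unused and replaced, counting it as zero avoids double counting. The 85.2% and 70.4% figures apply only to kits lost after use. The two rules are a stated convention rather than a contradiction.

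The consequence is also small. No analysis population in SAP 5.2 depends on compliance. The 80% figure in Protocol 6.4 is an example that prompts the site to consider discontinuation; the SAP does not apply it to this derived variable.

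None of this removes the core defect: the credit has no limit tied to the days available for dosing.

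**Conclusion.** The point holds as a minor defect in a derivation rule. As written, SAP 4.1.18 can credit tablets that could not have been taken, so compliance can exceed 100% in a dropout who stops soon after dispensing and does not return the last kit.

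The range from 206% on the Week 2 kit to 119% on the Week 18 kit rests on one kit per visit interval, full prior adherence, and termination dated at the last dose 3 days after dispensing. Relaxing these shrinks, removes or reverses the excess.

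The planned 27% dropout rate is a ceiling on the share of subjects who could be affected in this way, not an estimate, because the share with unreturned kits is not given. A between-arm bias is possible but cannot be sized. Only the descriptive compliance summary in SAP 5.8 changes; no efficacy or safety inference does.

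**What to change.** Replace the no-return-information rule in SAP 4.1.18 with one of these:

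1. For a kit with no return information, credit at most 3 tablets per day from dispensing to the earlier of the next dispensing or the last dose date on the EXPOSURE eCRF, less recorded missed doses. Count expected tablets for that kit over the same days.
2. Drop that kit's interval from both numerator and denominator.

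Treat lost kits the same way, unless the record shows that the kit was lost unused.

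The same days must be used on both sides; limiting the numerator alone would understate compliance. Option 1 still assumes full dosing apart from recorded misses, so option 2 is cleaner where the last dose date is uncertain.

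The cost is a short text change, minor programming and a slightly shorter evaluable interval. Last dose date is already collected.
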